1.3.1 Medicis Midface Volume Scale (MMVS)

MMVS is a four-point scale assesses the fullness of the midface from Fairly Full (1) to Substantial Loss of Fullness (4) as described below. The blinded evaluator will rate the subject's right and left midface for severity of volume deficiency using the MMVS at screening, baseline, 6, 9, 12, 18 and 24 months in Group A and Treatment Group, and at screening, baseline 6, 9 and 12 months in Control Group. The treating investigator will do the MMVS evaluation at all visits in each group. The blinded evaluator and treating investigator will conduct their MMVS assessments using a photographic scale.

Table 1. Medicis Midface Volume Scale

MMVS	
1	Fairly full midface; cheek prominence projected beyond the infraorbital rim at 45-degree view.
2	Mild loss of fullness in midface area; flatness of midface; cheek prominence at or behind infraorbital rim. May have slight presence of tear trough but not extending past mideye. Can start to see minimum volume loss of anterior cheek.
3	Moderate loss of fullness with slight hollowing below malar prominence; presence of the nasojugal groove extending past mideye.
4	Substantial loss of fullness in the midface area, clearly apparent hollowing below malar prominence; evidenced by significant indentation in the midface area.

1.3.2 3D Digital Imaging Analysis

The measurement of volume change in the midface (right and left combined) from baseline will be calculated by 3D digital image analysis at 6, 9, 12, 18 and 24 months in Group A and Treatment Group, and at 6, 9 and 12 months in Control Group.

1.3.3 Global Aesthetic Improvement Scale (GAIS)

The 5-graded Global Aesthetic Improvement Scale (GAIS) will be used to assess the aesthetic improvement of the midface fullness of both sides of the live subject as compared to photographs taken before treatment. Each midface side will be rated separately. The treating investigator and the subject will, independently of each other, respond to the question: "How would you describe the aesthetic improvement of the midface fullness for each side today compared to the photos taken before treatment?" GAIS will be assessed by treating investigator and subjects at each follow up visit.

 GALDERMA	Title 43CHSA1803 Statistical Analysis Plan - Sculptra China	Doc id MA-40407
--	---	---------------------------

Table 2. Global Aesthetic Improvement Scale

Rating	Definition (for treating investigator)
Very much improved	Optimal cosmetic result for the implant in this subject.
Much improved	Marked improvement in appearance from the original condition, but not completely optimal for this subject.
Improved	Obvious improvement in appearance from the original condition.
No change	The appearance is essentially the same as original condition.
Worse	The appearance is worse than the original condition.

1.3.4 Subject satisfaction questionnaire

Subjects will be asked about their satisfaction with the treatment outcome using a questionnaire at 6, 9, 12, 18 and 24 months in Group A and Treatment Group.

1). Do you think your Cheek Volume Deficit and/or Contour Deficiency has been improved with the treatment? Yes/No

2). Do you think that the overall result of the treatment looks natural? Yes/No

3). Would you say that the study treatment?

- Surpass your expectations
- Meet your expectations
- Do not meet your expectations
- You did not have any specific expectations before the injections

4). Do you think that the treatment brings you more? (*tick all boxes that apply*)

- Youth
- Beauty
- Harmony
- Symmetrical appearance
- Pep/Liveliness/Freshened look
- Self esteem /confidence

5). Would you say that you feel more attractive? Yes/No

6). How do you feel about yourself since the treatment was performed?

- Very much better
- Much better
- Somewhat better
- The Same
- Worse; if worse, please explain why:

7). Overall, how satisfied are you with the treatment result?

- Very satisfied
- Satisfied

 GALDERMA	Title 43CHSA1803 Statistical Analysis Plan - Sculptra China	Doc id MA-40407
--	---	---------------------------

2019-10-24 08:59

Effective date:

Effective

Version: 1.0

Somewhat satisfied
 Not satisfied

8). Did you get any feedback about your look from your family, friends, colleagues?

Positive feedback
 Negative feedback
 No feedback

9). Would you recommend this treatment to friends? Yes/No

10). Would you like to receive the same treatment again? Yes (exactly the same)/No

1.4 Effectiveness endpoints

1.4.1 Primary effectiveness endpoint

Percentage of responders, defined by at least 1 point improvement from baseline on the MMVS on both sides of the face concurrently, as measured by the blinded evaluator at 12 months in both Treatment Group and Control group.

1.4.2 Secondary effectiveness endpoints

- Percentage of responders, defined by at least 1 point improvement from baseline on the MMVS on both sides of the face concurrently, as measured by the blinded evaluator at 6, 9, 18 and 24 months in Treatment Group, and at 6 and 9 months in Control Group.
- Percentage of responders, defined by at least 1 point improvement from baseline on the MMVS on both sides of the face concurrently, as measured by the treating investigator at 6, 9, 12, 18 and 24 months in Treatment Group, and at 6, 9 and 12 months in Control Group.
- Volume change from baseline over time of the right and left midface areas combined, as measured by digital 3D photography at 6, 9, 12, 18 and 24 months in Treatment Group, and at 6, 9 and 12 months in Control Group.
- Percentage of responders, defined by having “Improved”, “Much improved” or “Very much improved” according to the Global Aesthetic Improvement Scale (GAIS) on both sides of the face combined, as assessed by the subject and the treating investigator at 6, 9, 12, 18 and 24 months in Treatment Group, and at 6, 9 and 12 months in Control Group.
- Percentage of subjects in each response category of each question in the subject satisfaction questionnaire in Treatment Group at 6, 9, 12, 18 and 24 months.

Note: Time of the Follow up visits at 6, 9, 12, 18 and 24 months is calculated from baseline/randomization.

1.5 Safety assessments

The methods for collecting safety data are described in Section 8 of the Clinical Study Protocol (MA-39381) and include assessments of anticipated injection related reactions as collected in Subject Diary, Adverse Events (AE) and Serious Adverse Events (SAE). Laboratory assessments will be performed at screening for all subjects. In Group A and Treatment Group, it will also be taken at 12 months visit or at early termination if termination occurs before 12 months visit.

	Title 43CHSA1803 Statistical Analysis Plan - Sculptra China	Doc id MA-40407
--	---	---------------------------

Effective date: 2019-10-24 08:59

A two-point scale (“Yes” or “No” response) will be used for the causality assessments of AE and SAE. The Treating Investigator should be asked to indicate a response to each of the following questions in the eCRF:

“Do you consider that there is a reasonable possibility that the event may have been caused by the study product?”

“Do you consider that there is a reasonable possibility that the event may have been caused by the study product injection procedure?”

If any of these questions is answered with a ‘Yes’, the AE will be considered related. These assessments will also be reviewed by the Sponsor. In the case of a disagreement, the AE will be classified as “Related”.

1.6 Safety endpoints

- Incidence, intensity, duration, and onset of adverse events (AEs) collected throughout the study.
- Incidence, intensity, and number of days of anticipated injection related reactions, collected using 4-week subject diaries after each treatment session for the Treatment Group.

Effective

Version: 1.0

	Title 43CHSA1803 Statistical Analysis Plan - Sculptra China	Doc id MA-40407
--	---	---------------------------

Effective date: 2019-10-24 08:59

Effective

Version: 1.0

2 Statistical Methods

2.1 General methods

All summaries for Group A and B will be done separately. The analyses described in the following sections primarily concern Group B. However, Group A will be analyzed in the same way, except that no hypothesis testing will be performed for Group A (there is only one treatment group in Group A), and the analyses will be done based on observed cases (i.e. no imputation of missing values will be done).

All statistical analyses, including summary tables and data listings, will be performed using the SAS® system (version 9.4 or later).

In general, effectiveness, safety, demography, subject characteristics, and treatment related variables will be presented using descriptive statistics. Continuous data will be summarized using n (number of observations), mean, standard deviation, median, minimum and maximum value, while categorical data will be presented by frequency and percentage. Graphs may be used as appropriate.

All statistical testing will be two-sided and performed at a significance level of 5%. Confidence intervals will be 2-sided and constructed using 95% confidence level.

If any SAP changes are needed before database lock (DBL), the SAP will be amended. Changes after DBL will be documented in the Clinical Study Report (CSR). If additional supportive or exploratory analyses are requested after SAP approval, this will not require amendment of the SAP, but these additional analyses will be described in the CSR. Some of the analyses detailed here may be more explicit or in some aspects different from those stated in the protocol. In case of differences, this SAP supersedes the statistical sections in the protocol.

All study data from the CRFs as well as derived variables will be provided in subject data listings.

2.2 Analysis Populations

The following populations will be defined:

- Safety
- Includes all subjects in Group B who were treated with Sculptra or randomized to no-treatment group. Subjects are analyzed based on the as treated principle.
- Full Analysis Set (FAS)
- Includes all subjects in Group B who were treated with Sculptra or randomized to no-treatment group. Subjects are analyzed according to the randomisation assignment.
- Per Protocol (PP)
- Includes all subjects in FAS that comply to the protocol procedures with no deviations that can affect the evaluation of the primary variable.

The FAS population is the primary population for all effectiveness analyses. All safety analyses will be based on the Safety population.

For Group A, all analyses will be performed based on all subjects.

 GALDERMA	Title 43CHSA1803 Statistical Analysis Plan - Sculptra China	Doc id MA-40407
--	---	---------------------------

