#### Treatment

Each subject assigned to Group A and Treatment Group will receive up to 4 injection sessions with 5( $\pm 1$ ) weeks (at least 4 weeks) intervals. Initial treatment will be on Day 1. Study treatments should be stopped if optimal midface augmentation has been obtained or a maximum of 4 injection sessions completed. Optimal midface augmentation is defined as the best possible aesthetic result that can be obtained for an individual study participant, as agreed upon by the treating investigator and subject.

Subjects assigned to the Control Group will not receive treatment during the study.

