#### 4.4.2 Blinding

Only the evaluator will be blinded, both treating investigator and subjects will be open-labelled.

The Blinded Evaluator shall not be allowed to retrieve study supplies or to be present during opening of the study supplies or injections. The Treating Investigator is not allowed to discuss treatments with the blinded evaluator or the subjects. All documents with information on study products shall be kept in a separate binder not available to the blinded evaluator.

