#### 4.8.1.2 Baseline (D1)

- Height and Weight
- Medical history/concurrent diseases
- Vital signs (before treatment, pulse rate, blood pressure, respiratory rate, body temperature)
- Inclusion and exclusion criteria
- Randomization
- Pregnancy test for childbearing potential women (before treatment)
- Photography (before treatment)
- MMVS (before treatment, by Blinded Evaluator and treating investigator)
- Treatment
- Dispense subject diary
- Concomitant medications /procedures
- Device deficiencies
- AE since last visit

If screening and baseline visit occur on the same day, the following procedures for baseline will not be repeated.

- Medical history/concurrent diseases
- Inclusion and exclusion criteria
- MMVS (before treatment, by Blinded Evaluator and treating investigator)
- Concomitant medications /procedures
- Pregnancy test for childbearing potential women(before treatment)
- AE since last visit

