### 8.2 Laboratory assessment

Laboratory samples for Haematology and Serum chemistry assessment will be taken at the screening visit (day -21 to day 1) for all subjects. In Group A and Treatment Group, it will also be taken at 12 months visit or at early termination if termination occurs before 12 months visit.

The following laboratory assessments will be performed:

- Haematology: haemoglobin, red blood cells, white blood cells, differential count and platelet count.
- Serum chemistry: renal function tests (creatinine and BUN); and liver function tests (aspartate amino transferase (ASAT), alanine amino transferase (ALAT) total bilirubin, direct bilirubin and indirect bilirubin).

Pregnancy test (Urine HCG) will be performed at screening, all injection visits (prior to treatment and the study completion/early termination for Group A and Treatment Group, and at screening for Control group, in all women of childbearing potential, including those currently using contraception. The test result must be negative for the subject to receive any treatment with study product.

Other laboratory test might be performed at the discretion of the investigator. All laboratory assays will be performed at a local laboratory. Reference ranges will be supplied by the

 GALDERMA	Title 43CHSA1803 Clinical Study Protocol	Doc id MA-39381
--	--	---------------------------

Effective date: 2019-06-20 00:56

Effective

Version: 2.0

laboratory and used by the Investigator to assess the laboratory data for clinical significance and out of range pathological changes.

The results of the hematology and serum chemistry will only be used for safety assessment by investigator and will not be collected in the eCRF. The pregnancy test for women of childbearing potential will be recorded in the eCRF.

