1.3 Effectiveness assessments

For all assessments regarding subjects in Group A and subjects in Treatment Group in Group B, baseline will be defined as the observation that is closest to but prior to study treatment on Day 1. Likewise, change from baseline will be calculated as the value at a given time point minus the baseline value. For the Control Group baseline is defined as the observation that is closest to but prior to randomization.

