2.4.2 Handling of missing data

Different assumptions regarding the missing data will be used. For the primary effectiveness analysis, missing values in the FAS will be assumed to be missing due to lack of effect. Therefore missing data up to the Month 12 visit will be imputed using the baseline observation carried forward (BOCF) method. As an alternative approach, missing data will be assumed to be unrelated to treatment effect. To impute data under this assumption, missing data up to the Month 12 visit will be imputed using the hot deck method. Both of these alternatives will estimate the effectiveness of the treatment policy (irrespective of use of not allowed treatments, procedures, or medications) rather than the true, clinical treatment effect.

To obtain an estimate of the true, clinical treatment effect, the primary effectiveness analysis will be performed using the PP population.

All other endpoints will be analysed on available data (observed cases - OC), i.e. no imputations will be done.

Use of Hot Deck

Each missing value in MMVS at Month 12 visit (recipient) will be imputed with a non-missing (observed) value from a subject randomly selected from the same imputation class (donor). Imputation classes will be defined based on treatment group (Sculptra or Control group), baseline MMVS value (2, 3 or 4 as assessed by the blinded evaluator) and age group (<55 vs. ≥ 55). Alternative imputation classes may be used if deemed necessary.

	Title 43CHSA1803 Statistical Analysis Plan - Sculptra China	Doc id MA-40407
--	---	---------------------------

Effective date: 2019-10-24 08:59

Effective

Version: 1.0

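### The FAS requires treatment in the Sculptra arm but only randomisation in the control arm, and no planned effectiveness analysis covers all randomised Group B subjects (effect likely small)

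*SAP*

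**What the plan says.** SAP 2.2, in the same words as Protocol 10.2, sets the FAS: "Includes all subjects in Group B who were treated with Sculptra or randomized to no-treatment group. Subjects are analyzed according to the randomisation assignment". The FAS is the primary population for all effectiveness analyses. PP is drawn from within it, and the Safety set has the same entry rule. SAP Table 3-19, the primary results table, has three blocks: FAS with BOCF, PP without imputation, and FAS with hot-deck imputation. All randomised subjects appear only in the disposition table (Table 3-3), which has separate rows for randomised and treated.

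SAP 2.4.2 describes the BOCF and hot-deck analyses thus: "Both of these alternatives will estimate the effectiveness of the treatment policy (irrespective of use of not allowed treatments, procedures, or medications", as opposed to a clinical effect that PP is meant to estimate.

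On timing and blinding, Protocol 4.1 states "Initial treatment will be on Day 1", and Protocol 4.4.2 says that "both treating investigator and subjects will be open-labelled". The Sculptra-arm baseline visit (Protocol 4.8.1.2) lists "Pregnancy test for childbearing potential women (before treatment", and Protocol 8.2 adds "The test result must be negative for the subject to receive any treatment with study product". Controls are tested for pregnancy only at screening.

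For the Treatment Group, SAP 1.3 ties baseline to the injection: "baseline will be defined as the observation that is closest to but prior to study treatment on Day 1". For controls it is the last value before randomisation.

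**The concern.** Being injected is an event after randomisation, and only one arm has to pass it to be analysed. Subjects and treating investigators know the allocation, so who goes uninjected can depend on it. A Sculptra early leaver vanishes from numerator and denominator. A control early leaver with no Month 12 value remains in the denominator as a non-responder. If similar shares leave both arms at that point, the control rate is pulled down and the Sculptra rate is not.

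The schedule contains one built-in route. Unless screening and baseline fall on the same day, a Sculptra subject can be randomised and then fail the pre-injection pregnancy test. No such step exists for controls.

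At stake is the single primary comparison of a registration study. The exclusion also sits poorly with a treatment-policy aim, although SAP 2.4.2 explains that aim only by non-allowed treatments, procedures and medications. That clash is arguable, not explicit.

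**Working it through.** **Inputs from the documents.** 126 and 63 randomised; 60% v 30% response; 20% drop-out (SAP 2.7); two-sided Fisher's exact test at 0.05 (SAP 2.4.3); missing Month 12 scored as non-response under BOCF (SAP 2.4.2).

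**Assumed, because the documents give no figure.** The numbers leaving between allocation and first injection, k1 (Sculptra) and k2 (control), all with Month 12 missing.

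**The plan's own figure.** At 100 v 50 and 60% v 30%, full enumeration of the two-sided Fisher test gives 92.7% power and the Walters arcsine approximation gives 91.8%, against the stated approximately 90%. Inflation gives 100/0.8 = 125 and 50/0.8 = 62.5, rounded to 63, against the stated 126 and 63. The sample size is not in question here.

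**Model.** Let a1 and a2 be the numbers able to respond, and p1 and p2 their response rates.
- As written: denominators 126−k1 and 63. Expected difference = a1·p1/(126−k1) − a2·p2/63.
- All randomised: denominators 126 and 63. Expected difference = a1·p1/126 − a2·p2/63.
- Chance of Sculptra success = sum over all (x, y) of Bin(x; a1, p1)·Bin(y; a2, p2), counting tables with Fisher p<0.05 and the higher rate on Sculptra.

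Model 1, no other drop-out: a1 = 126−k1, a2 = 63−k2. Model 2, 20% missing in total with the early leavers included: 25 and 13 missing, so a1 = 101 and a2 = 50, and the as-written result depends only on k1.

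**Worked case, k1/k2 = 3/2, at 60% v 30%.**
- Model 1, as written: 123×0.6/123 − 61×0.3/63 = 60.0 − 29.0 = 31.0 points. All randomised: 123×0.6/126 − 29.0 = 29.5 points.
- Model 2, as written: 101×0.6/123 − 50×0.3/63 = 49.3 − 23.8 = 25.5 points. All randomised: 101×0.6/126 − 23.8 = 24.3 points.

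**Results, as written v all randomised.**

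| k1/k2 | False Sculptra success at 30%/30%, Model 1 | Same, Model 2 | Difference at 60%/30% (points), Model 1 | Same, Model 2 |
|---|---|---|---|---|
| 2/1 | 2.3% v 2.1% | 2.05% v 1.7% | 30.5 v 29.5 | 25.1 v 24.3 |
| 3/2 | 2.6% v 2.2% | 2.25% v 1.7% | 31.0 v 29.5 | 25.5 v 24.3 |
| 6/3 | 2.95% v 2.0% | 2.7% v 1.7% | 31.4 v 28.6 | 26.7 v 24.3 |
| 13/6 (extreme) | 4.35% v 1.7% | 4.2% v 1.7% | 32.9 v 26.7 | 29.8 v 24.3 |

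With no early leavers, Model 1 gives 2.1% for both sets.

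**Exclusion alone.** With 13/0 and no other drop-out, false Sculptra success as written is 1.9%, no higher than the 2.1% with no leavers. The lean needs control early leavers, or other missing data, alongside the excluded Sculptra subjects.

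**Can a decision flip?** Two-sided Fisher p-values:
- 15/63 controls, 2 untreated: 49/124 gives 0.035; 49/126 gives 0.0501.
- 15/63 controls, 4 untreated: 47/122 gives 0.0497; 47/126 gives 0.072.
- 19/63 controls, 2 untreated: 57/124 gives 0.042; 57/126 gives 0.059.
- Planned effect, 13 untreated (0.6×113 ≈ 68 responders; 0.3×63 ≈ 19): 68/126 v 19/63 still gives 0.0021.

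**The case against.** The best case against has five parts.

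1. **The nominal error rate is kept.** Total two-sided error as written (Model 1) is 4.1% to 4.3% in the three main cases, and passes 5% (5.04%) only at 13/6. The chance that the two sets disagree on Sculptra success is 0.2% under no effect and 0.6% at 60%/30% for 2/1, and 0.4% and 0.7% for 3/2. This stands, and it is why the point is not graded higher.

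2. **Much of the lean comes from control leavers under BOCF, which the change leaves in place.** With no untreated Sculptra subjects, both sets give 2.84% (0/2), 3.27% (0/3) and 4.95% (0/6). Subjects seeking augmentation who learn they will not be treated are arguably the likelier leavers, and then the sets nearly coincide (1/3: 3.14% v 3.03%). This also stands. It is a reason to treat the arms alike, not a defence of dropping leavers from one arm only.

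3. **The pregnancy route is narrow.** Screening already includes a test at most 21 days earlier, and Protocol 8.3.7 keeps a pregnant subject in follow-up, so her Month 12 score may exist. True. Such a subject could be analysed with observed data, yet the present rule excludes her.

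4. **The remedy has a bad corner.** At 13/0 with no other drop-out, all-randomised analysis raises total two-sided error to 5.9% (4.05% as written), although false Sculptra success falls to 0.6% (from 1.9%).

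5. **A supportive row would be enough, and the protocol carries the same definition.** Table 3-3 and the listings also let a reader rework the BOCF result by hand if all untreated subjects have Month 12 missing. A supportive row would close the reporting gap. It would leave the primary test on a set chosen after open allocation. On the documents, SAP 2.1 settles precedence: "In case of differences, this SAP supersedes the statistical sections in the protocol".

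**Conclusion.** The concern holds. The entry rule differs by arm, and no pre-specified effectiveness analysis includes all randomised Group B subjects. The likely effect is small. For 2 to 6 untreated Sculptra subjects with about half as many control early leavers, the rule adds roughly 0.2 to 1.0 percentage points to the chance of a false Sculptra success and 0.8 to 2.8 points to the expected difference at the planned rates. It would not overturn a result near the planned effect, but it can decide a borderline one.

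These sizes rest on assumed leaver counts, on early leaving in both arms, and on Month 12 being missing for every early leaver. If every Sculptra subject is injected on Day 1, the two sets are identical. It should still be fixed: the exclusion is avoidable, acts after open allocation, and touches the primary test.

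**What to change.** Amend the SAP before database lock:

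- **SAP 2.2:** define the FAS as all randomised Group B subjects, analysed as randomised, using the observed Month 12 MMVS where it exists and BOCF otherwise in the primary analysis.
- **SAP 1.3:** for subjects randomised to Sculptra but not treated, take baseline as the last value before randomisation, the rule already used for controls.
- **Table 3-19:** keep the treated-only set as a supportive row.
- **SAP 2.8:** record the difference from Protocol 10.2.

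PP needs no edit, because SAP Table 3 already excludes subjects not treated as randomised. No new data are needed. Because the SAP takes precedence over the protocol's statistical sections, the analysis can change without a protocol amendment.

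The cost is a slightly lower Sculptra rate and some power. Power at 60%/30%, all randomised v as written:

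| k1/k2 | No other drop-out | 20% missing |
|---|---|---|
| 2/1 | 97.3% v 97.9% | 91.3% v 93.0% |
| 3/2 | 97.4% v 98.1% | 91.3% v 93.0% |
| 6/3 | 96.6% v 98.4% | 91.3% v 95.1% |
| 13/6 | 94.6% v 98.9% | 91.3% v 97.75% |

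Of the cases examined with no other drop-out or 20% missing in total, only the 13/0 worst case (no other drop-out) falls below the stated 90%: 87.9% v 96.8%.
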